11.2.5 Preexisting Medical Conditions

A preexisting medical condition is one that is present at the start of the study. Such conditions should be reported as medical and surgical history. A preexisting medical condition should be re-assessed throughout the trial and reported as an AE or SAE only if the frequency, severity, or character of the condition worsens during the study. When reporting such events, it is important to convey the concept that the preexisting condition has changed by including applicable descriptors (e.g., "more frequent headaches").

11.2.6 Pregnancy

Female Participants

The PATCH Trial

Participants should not become pregnant while on this study and for 90 days after last dose of study drug. In addition, participants should not breastfeed while on this study as these drugs may also affect a breast-feeding child. Pregnant women and women who are breast-feeding are not allowed to participate in this study. Participants must agree to use two medically accepted forms of birth control including condoms, diaphragms, cervical cap, an intra-uterine device (IUD), surgical sterility (tubal ligation or a partner that has undergone a vasectomy), or oral contraceptives, OR must agree to completely abstain from intercourse for at least two weeks before receiving first dose of study drug, during participation in this study and for 90 days after last dose of study drug. Abstinence at certain times of the cycle only, such as during the days of ovulation, after ovulation and withdrawal are not acceptable methods of birth control. Even when an approved contraceptive method is used, there is always a small risk that the participant could still become pregnant. Subjects must agree to self-report pregnancy to the study team during the 90 days after the last dose of study drug.

Male Participants

Participants should not father a child while on this study. If the participants spouse or partner has the potential to become pregnant, the participant and partner must use two medically accepted forms of birth control including condoms, diaphragms, cervical cap, an intra-uterine device (IUD), surgical sterility (vasectomy or a partner that has undergone a tubal ligation), or oral contraceptives, OR must agree to completely abstain from intercourse during participation in this study and for 90 days after last dose of study drug. If the partner is taking oral contraceptives, she must begin taking them at least two weeks before the participants first dose of study drug. Abstinence at certain times of the cycle only, such as during the days of ovulation, after ovulation and withdrawal are not acceptable methods of birth control.

If a female participant becomes pregnant while receiving investigational therapy or within 90 days after the last dose of study drug, she must agree to self-report the pregnancy to the clinical investigator. The clinical investigator must immediately notify sponsor-investigator (who will then notify Novartis/Sandoz) in accordance with SAE reporting guidelines. Follow-up to obtain the outcome of the pregnancy should also occur. Abortion, whether accidental, therapeutic, or spontaneous, should always be classified as serious, and expeditiously reported as an SAE. Similarly, details of the birth, and the presence or absence of any congenital anomaly/birth defect or maternal and/or newborn complications in a child born to a female participant exposed to the study drug should be reported as an SAE. Follow-up information regarding the course of the pregnancy, including perinatal and neonatal outcome and, where applicable, offspring information must be reported to the sponsor-investigator (and Novartis/ Sandoz). In order for sponsor-investigator or designee to collect any pregnancy surveillance information from the female participant a signed informed consent addendum for disclosure of this information must be obtained (and will be supplied to the IRB for review at the time the incidental pregnancy is encountered, not anticipated and therefore not included with the original protocol documents). Any pregnancy that occurs in a female partner of a male study participant should be reported. Information on this pregnancy will be collected on the Pregnancy Surveillance Form (supplied for IRB review in the event pregnancy in a female partner of a male participant is encountered). In order for sponsor-investigator or designee to collect any pregnancy surveillance information from the female partner, the female partner must sign an informed consent form for disclosure of this information (form to be supplied in the event such a pregnancy was to be encountered).

11.3 UPENN IRB Notification by Investigator-Sponsor

The University of Pennsylvania IRB (Penn IRB) requires expedited reporting of those events related to study participation that are unforeseen and indicate that participants or others are at increased risk of harm. The Penn IRB will not acknowledge safety reports or bulk adverse event submissions that do not meet the criteria outlined below. The Penn IRB requires researchers to submit reports of the following problems within 10 working days from the time the investigator becomes aware of the event:

- Any adverse event (regardless of whether the event is serious or non-serious, on-site or off-site) that occurs any time during or after the research study, which in the opinion of the principal investigator is:

Unexpected (An event is “unexpected” when its specificity and severity are not accurately reflected in the

Property of University of Pennsylvania
Confidential

The PATCH Trial

protocol-related documents, such as the IRB-approved research protocol, any applicable investigator brochure, and the current IRB-approved informed consent document and other relevant sources of information, such as product labeling and package inserts.)

AND

Related to the research procedures (An event is “related to the research procedures” if in the opinion of the principal investigator or sponsor, the event was more likely than not to be caused by the research procedures.)

Deaths occurring for patients on-study and within 30 days of study drug administration that are considered unforeseen and indicates participants or others are at increased risk of harm (i.e. unexpected and probably/definitely related), must be reported to the IRB within 24 hours of notification.

See: <https://irb.upenn.edu/> for additional reporting details.

11.3.1 Reporting Process to IRB at Penn.

Principal Investigators are encouraged to submit reports of unanticipated problems posing risks to participants or others using the form: “**Unanticipated Problems Posing Risks to Participants or Others Including Reportable Adverse Events**” via HS-ERA or a written report of the event within 7 working days. FDA Notification by Investigator-Sponsor.

This study is IND exempt and reporting to the FDA is voluntary using a MedWatch 3500 or via the FDA’s website for voluntary reporting.

11.4 Medical Monitoring

It is the responsibility of the Sponsor-Investigator to oversee the safety of the study at this site. This safety monitoring will include careful assessment and appropriate reporting of adverse events, as noted above. Medical monitoring by an independent clinician, [name], Department of Medicine, will include a regular assessment of the number and type of serious adverse events on a periodic basis.

11.5 Data Safety and Monitoring Board (DSMB)

DSMB Description

The Data and Safety Monitoring Board (DSMB) for the Prevention And Treatment of COVID-19 with Hydroxychloroquine (PATCH) trial has been selected by the Sponsor-Principal Investigator [name] and acts in an advisory capacity to [name] for the PATCH trial to monitor participant safety, data quality and evaluate the progress of the study. Operational details of the DSMB are provided in the PATCH trial DSMB Charter.

- This DSMB will consist of 5 members with expertise in statistics, clinical trials, infectious disease, cardiology. The DSMB chair may change the membership of the DSMB in consultation with the PI.
- Observers from other research committees at PENN can be invited to join the open session of the DSMB deliberation.
- This DSMB will be independent of the Sponsor, regulatory agencies, IRBs/ECs, and investigators.

Roles and Responsibilities

The primary charge of the DSMB is to monitor the study for subject safety. Formal DSMB safety reviews occur as outlined in the charter. Additional review may be required. The DSMB may monitor effectiveness outcomes to determine relative risk/benefit, futility, or for early termination due to overwhelming effectiveness.

The PATCH Trial

The primary safety endpoint as well as guidance for the conduct of analyses and guidelines/stopping rules are established in the protocol and are reviewed by the DSMB.

The DSMB may also review data related to study conduct. Data to be reviewed and listed in the DSMB reports may include: enrollment rates over time, time from last subject enrolled to date of report (indication of delay between treatment or follow-up and reporting), summary of protocol violations as specified in monitoring reports generated by the Office of Clinical Research (OCR), completeness of treatment and follow-up visit data, and follow-up duration for the population included in the report. Protocol deviations, SAE reports, and assistance in day to day medical decision making on study participants will be handled by the Medical Monitor [name] who is also a member of the DSMB. The DSM will in turn be able to review formal reports generated by the OCR monitor and the interim analysis reports generated by the Sponsor-Investigator and his team.

The DSMB:

- Meets as outlined in this charter
- Provides recommendations about continuing, modifying, and stopping the study
- Operates according to the procedures described in this charter

11.7 Study Monitoring Plan

This study will be monitored by the Principal Investigator and sub-investigators, as appropriate. Such monitoring will include at least weekly meetings of the study team to review accrual, toxicity, SAEs. Dose escalations and study finding. In addition, the PI will ensure that data are completed in a timely manner and he or his designee will review the data for accuracy, completeness and integrity. Further, the PI will view real-time toxicity and all laboratory results on an ongoing basis by accessing the Monitoring Report database and the Protocol Labs database.

11.8 Auditing and Inspecting

The Investigator is required to permit direct access to the facilities where the study takes place, source documents, CRFs and applicable supporting records of study subject participation for audits and inspections by IRB, regulatory authorities (FDA) and academic authorized representatives (OCR). The Investigator will make every effort to be available for the audits and/or inspections.

12.0 Sample collection and processing for Correlative Science

[figure not shown]

Fig. 2. PATCH Sample Flow

12.1 Research Specimen Process, Banking and Analysis

Blood and oral fluid specimens collected as delineated in 9.0 Schedule of Events. Samples will be assigned a unique identified and then processed and frozen as per SOP within a BSL2+ space that is approved by the University of Pennsylvania’s Environmental Health and Radiation Safety (EHRS) program. The processed samples will be stored in the University of Pennsylvania within locked and temperature monitored freezers, and sample tracking. Documentation for sample receipt and processing will be collected and stored in either locked cabinet for paper records or within an encrypted and password protected database. The planned research analyses outlined in the exploratory objectives will be performed using qualified and if possible validated methods; however, due to nature of these research procedures, they may not conform to principles of good clinical laboratory practice.

13.0 STATISTICAL CONSIDERATIONS

13.1 Sample size calculation

Because we are uncertain about the outcome values for both control and treatment arms of the study, we will use group-sequential methods, initially proposing a real difference that is small, and allowing us to stop early for both efficacy and futility. We conduct two interim analyses and a final analysis, after approximately 1/3, 2/3, and 100% of subjects have completed. We will use the Hwang-Shih-DeCani alpha spending rules. Boundaries for efficacy and futility decisions are show below. Futility boundaries are non-binding.

z-value	Boundaries		Information Proportion
	Stage Efficacy	Futility	
1	2.7819	-0.8235	0.3400

The PATCH Trial			
	p-value	Boundaries	Information
Stage	Efficacy	Futility	Proportion
2	2.2653	0.4262	0.6800
3	1.6813	1.6813	1.0000
1	0.00270	0.79490	0.3400
2	0.01175	0.33497	0.6800
3	0.04636	0.04636	1.0000

Because we are uncertain about the outcome values for both control and treatment arms of the study, we will use group-sequential methods, initially proposing a real difference that is small, and allowing us to stop early for both efficacy and futility. We conduct two interim analyses and a final analysis, after approximately 1/3, 2/3, and 100% of subjects have completed. We will use the Hwang-Shih-DeCani alpha spending rules. Boundaries for efficacy and futility decisions are show below. Futility boundaries are non-binding.

Sub-Study 1, Home quarantined patients with COVID-19: The first date of quarantine will be considered the date of SARS-CoV-2 nasopharyngeal swab test that confirmed positivity.

The CDC guidelines for release from quarantine change during the course of this study. The original criteria were: 1) 72 hours without a fever 2) improvement in symptoms 3) 7 days since the beginning of symptoms have elapsed. The new criteria are: 1) 72 hours without a fever 2) improvement in symptoms 3) 10 days since the beginning of symptoms have elapsed. Our original sample size calculation was as follows:

Given the median duration of viremia is 14-20 days in mild cases, we will assume the null hypothesis that in the placebo cohort the median time to release from quarantine is 10 days from receiving a positive test. In order for HCQ to be considered more effective in this treatment setting we aim to see a median time to release from quarantine of 5 days. These values correspond to daily hazard rates of 0.069 and 0.139 respectively. We will randomize 1:1 HCQ to control and with 100 patients with 50 in the placebo arm and 50 in the HCQ arm. The one-sided z- test (alpha=.05) will have an overall 95% power to detect a significant difference between the two groups with medians of 10 and 5 days.

Based on the new CDC guidelines for quarantine release we will modify the analysis as follows: Given the median duration of viremia is 14-28 days in mild cases, we will assume the null hypothesis that in the placebo cohort the median time to release from quarantine is 14 days from receiving a positive test. In order for HCQ to be considered more effective in this treatment setting we aim to see a median time to release from quarantine of 7 days. These values correspond to daily hazard rates of 0.048 and 0.094 respectively. We will randomize 1:1 HCQ to control and with 100 patients with 50 in the placebo arm and 50 in the HCQ arm. The one-sided z- test (alpha=.05) will have an overall 93% power to detect a significant difference between the two groups with medians of 14 and 7 days.

The *hypothesis* will be tested using a one-sided test, with a z-score corresponds to the log of the hazard-ratio for recovery between the two groups. We will obtain estimates of the hazard ratio and group median survival, and 95% CI, from Cox regression. As a secondary analysis, we will stratify the analysis, and obtain separate estimates of the hazard-ratio by group. However, we are not powered to test the interaction for significance, and we do not expect significance within group.

Given that 20 subjects were recruited and treated under the old CDC guidance, we will conduct a primary analysis based on the updated 10-days from onset criterion. For the subjects who were released under the old criterion, this number will be constructed by assessing when a patient would have been released under the new rules. We will follow that with additional secondary analyses to assess the sensitivity of the results to the change in

The PATCH Trial

recommendations. These secondary analyses will include a) an analysis using mixed patients as released by the recommendation that was in place at the time, b) a stratified analysis, and c) an analysis of constructed release time based on the original 7-days from onset recommendation. We anticipate that these will yield similar results and that the conclusions will be insensitive to the changes made by the CDC.

Interim analysis: We will perform two interim analyses targeting 34% and 68% completion of participant enrollment, testing for early efficacy or futility, using z-score boundaries that follow Hwang-Shih-DeCani alpha spending rules. The determination of information for survival analysis is somewhat imprecise during the planning stages; for that reason, we will conduct analyses when 34% and 68% of the final sample have had 10 days of follow-up, and determine boundaries based on actual information available at analysis time. Following those rules, we have 93% power using 100% of the sample, if our under our 7 days versus 14 days scenario is true. Under those circumstances, we expect to have a 30% chance of stopping for early efficacy at the first interim analysis. We also have a 40% chance of stopping early for efficacy at the first interim analysis if the placebo arm really had 16 days median time instead of 14 days. Under normal circumstances (14 days v 7 days), we have a 48% chance of stopping for early efficacy at the second interim analysis. We also have a 63% chance of stopping early for efficacy at the second interim analysis if the placebo arm really has 16 days median time instead of 14.

Z-Value Boundaries

Maximum Information: 2000.1128

Alternative Hypothesis: $h_1 - h_2 < 0$ (one-sided)

Futility Boundaries: Non-Binding

Stage	Boundaries		Time Proportion	Time	Information Proportion
	Efficacy	Futility			
1	-2.7370	0.7159	0.4000	24.00	0.3660
2	-2.2814	-0.3990	0.6300	37.80	0.6740
3	-1.6808	-1.6808	1.0000	60.00	1.0000

P-Value Boundaries

Maximum Information: 2000.1128

Alternative Hypothesis: $h_1 - h_2 < 0$ (one-sided)

Futility Boundaries: Non-Binding

P-value boundaries are one-sided values.

Stage	Boundaries		Time Proportion	Time	Information Proportion
	Efficacy	Futility			
1	0.00310	0.76297	0.4000	24.00	0.3660
2	0.01126	0.34494	0.6300	37.80	0.6740
3	0.04640	0.04640	1.0000	60.00	1.0000

Sub-Study 3, prophylaxis in hospital workers: The transmission of SARS-COV2 from patient to hospital worker depends on many factors including specifics of standard care to prevent transmission, but especially on the number of patients seen at a given hospital or outpatient practice. Across China the reported hospital worker infection rate is 3.8%, but in Wuhan it is reported as 58% at the height of the epidemic. We will use a

10% transmission rate as the null hypothesis (low dose group). In order for HCQ to be considered effective our alternative hypothesis will be a 1% transmission rate. With a 1:1 randomization for the HCQ to control arms we would require a total of 200 hospital worker subjects total for Arm 4. With the placebo group of 100 subjects and the h HCQ arm of 100 subjects, a one-sided z-test ($\alpha=0.05$) comparing the rates in the two groups would have an 80% power to detect a significant difference when the difference in the population rates

The *PATCH Trial* is at least 9%.

The *hypothesis* will be tested using a one-sided test, with a z-score corresponds to the log of the odds-ratio for recovery between the two groups. We will obtain the estimate of the odds ratio, and 95% CI, from logistic regression.

Interim analysis: We will perform two interim analyses at 25% and 50% completion of participant enrollment, testing for early efficacy or futility, using z-score boundaries that follow Hwang-Shih-DeCani alpha spending rules. Following those rules, we have 84% power using 100% of the sample, if our under our 10% versus 1% scenario is true. Under those circumstances, we have a 6% chance of stopping for early efficacy at the first interim analysis. We also have an 81% chance of stopping early for efficacy at the first interim analysis if the low dose arm really has 45% infection instead of 10%. Under normal circumstances (10% v 1%), we have a 27% chance of stopping for early efficacy at the second interim analysis. We also have an 80% chance of stopping early for efficacy at the second interim analysis if the low dose arm really has 23% infection instead of 10%.

In addition, at our second interim analysis for SS3, we will evaluate the conditional power based on our original assumptions. The actual effect size for this study is completely unknown. If the effect size is smaller than we anticipated but still promising, and our conditional power falls between 0.5 and 0.8, we will consider formally adjusting the sample size in SS3 to achieve a conditional power of 0.8 based on an updated understanding of the effect size (29).

Z-Value Boundaries			
	Boundaries		Information
Stage	Efficacy	Futility	Proportion
1	2.9473	-1.2318	0.2500
2	2.5825	-0.2676	0.5000
3	1.6664	1.6664	1.0000

P-Value Boundaries			
	Boundaries		Information
Stage	Efficacy	Futility	Proportion
1	0.00160	0.89099	0.2500
2	0.00491	0.60550	0.5000
3	0.04782	0.04782	1.0000

12.2 Analysis of Secondary Endpoints.

Secondary outcomes will at least be analyzed as summary statistics, with group means, odds-ratios, and 95% CIs. We may conduct exploratory analyses using regression methods appropriate for each type of measure.

Sub-Study 1: Rate of secondary infection of housemates is a binomial count by household. We will summarize the proportion or rate by group, with 95% CI. With sufficient data, we will explore subgroups, patient, and secondary patient characteristics using logistic regression. Rate of hospitalization is a binary measure. We will summarize rates by group, and estimate the odds-ratio for treatment. Adverse event rates will be summarized as a count by subject, and mean count by group, and we will estimate a rate-ratio for treatment.

Sub-Study 3: For hospital employees, Adverse event rates will be summarized as a count by subject, and mean count by group, and we will estimate a rate-ratio for treatment.

REFERENCES

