3.1.2 Competent and capable to sign informed consent

3.1.3 Subjects meeting the following criteria by arm:

3.1.3 Sub-Study 1:

- Age ≥40 years since the risk of prolonged disease that progresses to severe COVID-19 disease increases with age.
- PCR-positive for the SARS-CoV2 virus
- Fever or cough or shortness of breath
- ≤4 days since the first symptoms of COVID-19 and date of testing
- Not requiring hospitalization and is sent home for quarantine.
- Not taking azithromycin at the time of enrollment
- Symptomatic at the time of enrollment
- Must live within 30 miles of HUP or Penn Presbyterian Medical Center to facilitate drop-off of medication
- Must have access to a working computer, or smartphone and have internet access
- Must be willing to fill out a daily symptom diary
- Must be available for a daily phone call,
- Must take their own temperature twice a day
- Must be willing to report the observed symptoms and development of COVID-19 in the co-inhabitants of the residence at which the quarantine will be served.

Sub-Study 3 Health Care Worker Prevention

- Healthcare worker at HUP or PPMC (Healthcare worker is defined as: a UPHS employee that physically interact with COVID-19 patients e.g., doctors, nurses, respiratory techs, certified nursing assistants, emergency room techs, OB ultrasound techs).
- ≥20 hours per week of clinical work scheduled in the coming 2 months during the COVID-19 pandemic
- No fever, cough, or shortness of breath in the past 2 weeks unless a SARS-CoV-2 test was performed for these symptoms and the result was negative prior to enrollment

The PATCH Trial

- 3.1.4 Sub-studies 1 and 3: Willing to report compliance with HCQ in the form of a diary
- 3.1.5 Sub-Studies 1 and 3: Participants are willing to collect oral fluid using a simple applicator that is provided, and freeze these samples.
- 3.1.6 Not pregnant and/or breastfeeding, as determined below:
Sub-Study 1 and 3: Not known to be pregnant or breast feeding as determined through self-report

[All participants] 3.1.7 Patients must be able to swallow and retain oral medication and must not have any clinically significant gastrointestinal abnormalities that may alter absorption such as, but not limited to malabsorption syndrome, major resection of the stomach or bowels, gastric bypass, lap banding.

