10.2 Response Criteria

Sub-Study 1: Time to release from quarantine. The criterion is afebrile for 72 hours AND improvement of symptoms AND at least 7 or 10 days have passed since symptoms started (according to contemporary CDC guidelines). To quantitatively assess improvement of symptoms the grading system in Section 8.5 will be used.

The PATCH Trial

May 2020. There was a change in CDC guidelines on quarantine time following onset of symptoms, changing from 7 to 10 days. We have adopted the new guidelines, but some of the earlier patients enrolled in the study were released in a shorter time than they would have been under the new guidelines. Because the response is time to release, we will record both release dates for each patient. While the release based on 10 days will be the primary outcome, we will run a parallel analysis of the 7-day measure as part of a sensitivity analysis.

Sub-Study 3: Measurement of SARS-CoV-2 positivity defined by PCR. Time to infection will be defined as the time in days from enrollment on the study to time to COVID-19 symptoms.

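### Sub-Study 1's amended 14 v 7 day design still carries the information and boundary table of the superseded 10 v 5 design, and its stopping chances, hazards and time origin do not agree with one another

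*Protocol*

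**What the plan says.** All references are to the final protocol unless stated.

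- **Outcome.** Section 13.1 gives the new release criteria, the third being "3) 10 days since the beginning of symptoms have elapsed". Section 10.2 confirms: "While the release based on 10 days will be the primary outcome".
- **Time origin.** Sections 2.1 and 13.1: "The first date of quarantine will be considered the date of SARS-CoV-2 nasopharyngeal swab test that confirmed positivity". The sample-size text a few lines later counts differently: "the median time to release from quarantine is 14 days from receiving a positive test".
- **Eligibility.** Section 3.1.3 (Sub-Study 1) allows at most 4 "days since the first symptoms of COVID-19 and date of testing".
- **Alternative.** Section 13.1: "we aim to see a median time to release from quarantine of 7 days", with daily hazards of 0.048 (placebo) and 0.094 (HCQ), 50 patients per arm, one-sided alpha 0.05 and 93% power.
- **Test.** One-sided, "with a z-score corresponds to the log of the hazard-ratio for recovery between the two groups".
- **Interim analyses.** Looks come when 34% and 68% of the sample have 10 days of follow-up, with boundaries set from the information actually available. The stopping chances are 30% (first look) and 48% (second look) for 14 v 7, and 40% and 63% for 16 v 7. The table printed below them gives maximum information 2000.1128 for a difference in hazards, looks at days 24, 37.8 and 60, fractions 0.3660 and 0.6740, and efficacy boundaries of 2.7370, 2.2814 and 1.6808 in absolute value.
- **Original protocol, section 13.1.** The same table, entry for entry, accompanies the 10 v 5 day design, with 95% power and stopping chances of 18% and 63%.

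**The concern.** The amendment changed the medians, the power and the stopping chances but not the table that should follow from them. The hazards and the 7-day target also sit uneasily with the new 10-day rule.

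The supplement's introduction says that Sub-Study 1 is still enrolling, and the DSMB is told that the stopping guidelines are those in the protocol. It would be working from a maximum information, boundaries and stopping chances that do not come from one design. Resetting boundaries from actual information also needs a planned maximum as denominator. The only one printed for this sub-study belongs to another design and is on a scale that the test does not use.

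**Working it through.** **1. Where the printed table comes from.** Inputs: 50 per arm, looks at days 24/37.8/60, exponential release times, uniform accrual over R days. R is not stated. Expected events per arm by day t are d = (50/R) × ∫ from 0 to min(t,R) of [1 − exp(−h(t − u))] du. Information on h1 − h0 is 1/(h1²/d1 + h0²/d0).

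- 10 v 5, R = 45 (the value that reproduces the table): 732.0, 1348.0, 2000.11. Fractions 0.366 and 0.674. Hwang-Shih-DeCani spending with gamma −4 returns 2.737/2.281/1.681. This is the printed table.
- 14 v 7, R = 45: 1225.1, 2367.6, 3744.7. Fractions 0.327 and 0.632, boundaries 2.80/2.35/1.68. With R from 60 down to 30 days the maximum runs from 3250 to 3922.

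To see the size of the mismatch: the 14 v 7 first look would be read as 1225/2000 = 0.61 of the information if the printed maximum were the denominator, against 0.327.

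**2. Power.** A three-look calculation on the log hazard-ratio scale (R = 45) gives 94.3% from the exact medians and 92.8% from the stated hazards. The hazard-difference scale gives 91.4%. The stated 93% is sound.

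**3. Stopping chances.** On the printed table, 93% power corresponds to a drift of 3.142. The first look is then 1 − Φ(2.737 − 3.142 × √0.366) = 1 − Φ(0.836) = 20%.

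| | Look 1 | At look 2 | Cumulative | Power |
|---|---|---|---|---|
| Protocol, 14 v 7 | 30% | 48% | not stated | 93% |
| Printed table at 93% power | 20.1% | 42.3% | 62.5% | 93% |
| 14 v 7, days 24/37.8/60, R = 31 (assumed) | 30.8% | 48.4% | 79.2% | 92.3% |
| Protocol, 16 v 7 | 40% | 63% | not stated | not stated |
| 16 v 7, same run, R = 31 | 42.5% | 47% | 89% | 97.1% |

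A 30% first look on the printed table would need 97.7% power. The R = 31 run (hazard-difference scale) accounts for 30%, 48%, 93% and roughly 40%, but not 63%. If both 16 v 7 figures were per-look, they would total 40% + 63% = 103%. The basis also seems to shift between documents. The original protocol's 18% and 63% for 10 v 5 match its table only if the second is cumulative (computed 19.4% and 61.1%), whereas the amended 48% matches as a per-look chance.

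The R = 31 run does not meet the protocol's own triggers. With uniform accrual these fall at 0.34 × 31 + 10 = day 20.5 and 0.68 × 31 + 10 = day 31.1, not days 24 and 37.8.

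**4. Hazards.** ln2/0.048 = 14.4 days and ln2/0.094 = 7.4 days, with ratio 0.094/0.048 = 1.96. Medians of 14 and 7 need 0.0495 and 0.0990. The 10 v 5 hazards are right: ln2/0.069 = 10.0 and ln2/0.139 = 5.0.

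**5. The release floor.** From the swab date, the earliest release is 10 minus the onset-to-swab lag: day 10, 9, 8, 7 or 6 for lags of 0, 1, 2, 3 or 4 days.

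- A constant hazard of 0.094 puts 1 − exp(−6 × 0.094) = 43% of HCQ releases before day 6, when none can occur. For placebo it is 1 − exp(−6 × 0.048) = 25%.
- A 7-day HCQ median needs at least half the arm to have lags of 3 or 4 days and to be released at or near the earliest date. If lags were spread evenly over 0 to 4 days (assumed), at most 2/5 = 40% could be out by day 7.
- If time ran from the result, and the result took 1, 2 or 3 days (assumed), that 40% would become 60%, 80% or 100%.

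**The case against.** The strongest reply is that the printed table decides nothing. Section 13.1 concedes that planning information is imprecise and sets boundaries from the information in hand. That stands, and it limits the point to planning figures and what the DSMB is told. It does not make a table from another design correct.

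Four stronger readings are tempting, and the documents do not support them.

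- *The 7-day median is impossible.* It is an arm median, the lag distribution is not given, and it lies inside the 6-to-10-day floor. The phrase "the median time to release from quarantine is 14 days from receiving a positive test" may also denote a later clock, which lowers the floor.
- *A true hazard ratio of 2 would be read as a failure against 14 v 7.* Success is judged on the log hazard ratio, not on a difference in medians. With a 14-day placebo median and everyone at one lag, the HCQ median ranges from 12 to 7 days depending on lag and model, so the gain runs from 2 to 7 days.
- *The stopping chances have no basis.* All but the 63% fit one 14 v 7 run. What is missing is its accrual assumption.
- *Power or type I error is compromised.* Power reproduces. The printed boundaries spend 0.05 in total at their own fractions, and they are to be reset anyway.

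The general 0.34/0.68 table at the head of section 13.1 does not rescue the 30%. With about the same drift it gives 1 − Φ(2.7819 − 3.14 × √0.34) = 17%.

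**Conclusion.** The point holds as a set of planning errors that can be corrected without touching the trial.

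- **Certain on the face of the documents:** the table is that of the 10 v 5 design, it is on the hazard-difference scale while the test uses the log hazard ratio, the hazards do not match the medians, and two time origins are in use.
- **Established by calculation:** maximum information is understated by nearly half (2000 against about 3745, or 3250 to 3922 over 60 to 30 days' accrual). The first-look chance under the printed table is about 20%, not 30%. The 63% for 16 v 7 agrees with no reading of the run that fits the other figures. The 45- and 31-day accruals are back-fitted, not stated.
- **Conditional on the swab-date clock:** constant hazards contradict the outcome, and the 7-day median is barely attainable rather than excluded.

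The power of about 93% for a hazard ratio near 2, the endpoint and the sample size are not in question. Type I error is not shown to be affected.

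**What to change.** 1. Replace the Sub-Study 1 table with one 14 v 7 run on the log hazard-ratio scale, with information in events, a stated accrual period, and look times that follow from the 34% and 68% triggers. Failing that, label the present table as the 10 v 5 design. The accrual should be realistic. The protocol says "Given that 20 subjects were recruited and treated under the old CDC guidance"; if those 20 came in over the 29 to 52 days from the 2 April approval to between 1 and 24 May, 100 patients would take 145 to 260 days.
2. Recompute every stopping chance from that run, say whether each is per-look or cumulative, and correct the 63%.
3. Correct the hazards to 0.0495 and 0.0990.
4. Use one time origin throughout section 13.1.
5. State the alternative primarily as a hazard ratio of 2. Give medians attainable under the 10-day floor as illustration, with the lag assumption stated. For a 14-day placebo median and evenly spread lags, the HCQ median is about 9.9 days (later of floor and exponential) to 11.2 days (floor plus exponential).

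Keep the rule that boundaries are reset from actual information. The cost is a recalculation and amended wording. Endpoint, sample size, procedures and conduct do not change, though the illustrative gain in days will probably look smaller.
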